6.8. Power and sample size considerations

In a two one-sided tests analysis for additive equivalence of paired means with bounds -0.11 and 0.11

for the mean difference in HAQ and a significance level of 0.05, assuming a mean difference of 0

HAQ points, a common standard deviation of 0.62 HAQ points and correlation 0.95 (between

measures), a sample size of 36 pairs (12 patients with each condition) is required to obtain a power

of at least 0.9. The actual power is 90.2%.

Minimal sample size: based on the same assumptions as above a sample size of 29 pairs (in total) is

required to obtain a power of at least 0.8 (80.7%).

It was decided by the steering committee for this study, that in order to at least attempt to explore

equivalence margins, within each disease group (i.e. RA, PsA and SpA) separately, a sample size of

20 pairs of each disease group would be feasible; i.e. enrolling 60 patients in total (corresponding to

a power of 99.2%).

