To evaluate whether electronic reporting of PROMs through a smartphone app is comparable to the standard touchscreen solution in the rheumatology outpatient clinic among patients with RA, PsA and axSpA in standard clinical care.

Hypothesis

Use of a smartphone app for registration of PROMs in rheumatology yields comparable results with the standard touchscreen solution in the outpatient clinic.

Objectives

Primary objective

To demonstrate a reasonably equivalent* self-reported disability status determined by the HAQ-DI score when using a smartphone app compared to the standard touchscreen solution among patients with inflammatory arthritis enrolled in a randomised, crossover, agreement study.

*Equivalence of HAQ-DI disability status will be concluded if the 95% confidence interval for monitoring difference is within ± 0.11 HAQ-DI score points.

Secondary objectives

To evaluate whether electronic reporting of VAS (Visual Analog Scale) pain, VAS fatigue, VAS global assessment, Patient Acceptable Symptom State (PASS), anchoring question, Bath Ankylosing Spondylitis Disease Activity Index (BASDAI) and Bath Ankylosing Spondylitis Functional Index (BASFI) through a smartphone app is reasonably comparable to the standard touchscreen solution in the rheumatology outpatient clinic among patients with inflammatory arthritis. In addition, to explore whether the electronic reporting of PROMs through a smartphone app is comparable to the standard touchscreen solution in the rheumatology outpatient clinic when stratifying by diagnosis (RA, PsA or axSpA). Additionally, to evaluate whether the participants prefer reporting PROMs electronically through the DANBIO app or the standard touchscreen solution in the rheumatology outpatient clinic.

Section 3: Study Methods

Trial design

The trial is a randomised, within-participant, crossover design including patients with RA, PsA and axSpA. In a crossover study, each participant acts as his/her own control for the questionnaire comparisons; thus, each patient answered the PROM questionnaires through the DANBIO app and the touchscreen in a randomised order at two consecutive time periods. The PROM questionnaires answered in the DANBIO app was exactly the same questionnaires as the participant answered on the touchscreen in the outpatient clinic.

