The sample size was based on the following assumptions: in a two one-sided tests analysis for additive equivalence of paired means with bounds -0.11 and 0.11 for the mean difference in HAQ-DI and a significance level of 0.05, assuming a mean difference of 0 HAQ-DI points, a common standard deviation of 0.62 HAQ-DI points (7) and correlation 0.95 (between measures), a sample size of 36 pairs (12 patients with each condition) were required to obtain a power of at least 90%.

Minimal sample size: based on the same assumptions as above a sample size of 29 pairs in total (10 patients with each condition) was required to obtain a power of at least 80%. It was decided by the steering committee for this study, that in order to at least attempt to explore equivalence margins within each disease group (i.e. RA, PsA and axSpA) separately, a sample size of 20 pairs of each disease group would be feasible; i.e. enrolling 60 patients in total (corresponding to a power of 99.2%).

Framework

Although the main objective is to explore similarity between PROM devises, the precision of the estimates will be derived from a superiority analysis framework. The objective of this crossover trial is to evaluate whether electronic reporting of HAQ-DI, VAS pain, VAS fatigue, VAS global assessment, PASS, anchoring question, BASDAI and BASFI through the DANBIO app is comparable to the standard touchscreen solution in the outpatient clinics among patients with inflammatory arthritis. Furthermore, to evaluate whether electronic reporting of PROMs through the DANBIO app is comparable to the standard touchscreen solution in the outpatient clinic stratifying by diagnosis (RA, PsA or axSpA). Thus, in the outcomes listed above we will test for equivalence.

Additionally, this study will evaluate whether the participants prefer reporting PROMs electronically through the DANBIO app or the standard touchscreen solution in the outpatient clinic. Hence, this outcome will be tested for superiority.

Statistical interim analyses and stopping guidance

No interim analyses were performed during this trial; no data analyses will be done before closure of the final SAP.

Timing of final analysis

Final analysis will be performed collectively as all outcomes are short-term outcomes.

Timing of outcome assessments

The timing of outcome assessments is illustrated below in Table 1:

Table 1: Overview of time points for PROM data registration in the DANBIO-App trial

ction	

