Data will be analysed using SAS Proc Mixed. The MIXED procedure fits a variety of mixed linear models. A mixed linear model is a generalization of the general linear model (GLM); the generalization being that the data are permitted to exhibit correlation (i.e., from two measures on the same participant). Repeated measures from the same individuals included maximum likelihood models, analysed using mixed models enables valid inference even with missing data from individuals having only some of their outcome measures observed (9). Having a continuous outcome as the

dependent variable (e.g. HAQ-DI), our modelling component of SAS PROC MIXED will include both fixed (period [I or II]; questionnaire [App Device or Touchscreen Solution]; rheumatic condition [RA or PsA or axSpA]) and random participant (i: 1, 2, 3,, n = 60) effects.

All analyses will be adjusted for the PROM-level at enrolment covariate i.e. the last DANBIO registration of the outcome (e.g. HAQ-DI) prior to enrolment in this trial.

Statistical interpretation of agreement

According to Piaggio et al. (10), equivalence is declared if the entire 2-sided 95%CI is included within the equivalence margin. Therefore, in this study a 2-sided 95% CI for the paired difference in each individual PROM (e.g HAQ-DI) will be derived from the mixed linear model and agreement will be declared if the 95% CI of difference between PROMs is within the prespecified equivalence range (e.g., -0.11 HAQ-DI-points to +0.11 HAQ-DI-points). These margins (see Table 2, above) are based on half of the effect that is usually considered a clinically relevant reduction in the individual PROMs. Thus, based on a superiority approach it was decided *a priori* that a 95% CI excluding differences between groups of greater than half the MID/MCID units would be interpreted as indicating the absence of a clinically meaningful difference (agreement) (6).

Missing data

In case of missing data for some of the participants, PROC MIXED handles the missing values implicitly adjusting for the missing values; unlike a GLM approach a mixed linear model uses the data for the periods where there is data and ignores the periods for which there is no data (11). Provided the data are "missing at random" (MAR), the estimates from PROC MIXED are valid (12). Imputations will not be used to replace missing data in the primary analyses, but will potentially be included in a sensitivity analysis to assess the impact/robustness of the conclusions.

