Additional analyses

The following pre-specified subgroup analyses will be performed on HAQ-DI to identify potentially important contextual factors. Given the relatively small numbers of participants to be recruited and the gender predominance in both RA and AS, such pre-specified subgroup analyses is likely not adequately powered. Thus, the following potentially important subgroups will be explored by using stratified analyses, using a p < 0.10 as being potentially important:

Female sex versus male sex

- RA versus other (i.e. PsA or axSpA)
- The younger half of the trial group versus the older half (median for each diagnosis)
- Age > 65 years versus age \leq 65 years (e.g. participants with anticipated IT-experience)
- Duration of data registration > 30 minutes (i.e. longer than anticipated) versus duration of data registration ≤ 30 minutes

Harms and adverse events

This study only tests the DANBIO app against the touchscreen solution in the outpatient clinic among patients with inflammatory arthritis; thus, the trial has no influence on the patient's current or future arthritis treatment. Consequently, safety data will not be collected during the course of this trial.

Statistical software

Data will be analysed using SAS Proc Mixed. The MIXED procedure fits a variety of mixed linear models.

References

- 2. DANBIO. Om DANBIO, Baggrund og historie [Internet]. [cited 2019 Jun 25]. Available from: https://danbio-online.dk/om-danbio/baggrund
- Zochling J. Measures of symptoms and disease status in ankylosing spondylitis: Ankylosing Spondylitis Disease Activity Score (ASDAS), Ankylosing Spondylitis Quality of Life Scale (ASQOL), Bath Ankylosing Spondylitis Disease Activity Index (BASDAI), Bath Ankylosing Sp. Arthritis Care Res. 2011;63:47–58.

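### Comparability is promised for RA, PsA and axSpA separately, but no specified analysis gives a HAQ-DI app–touchscreen difference for PsA alone or axSpA alone

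*Protocol*

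**What the plan says.** The SAP is bound into the protocol file after Appendix 8, so both can be read together.

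**What is promised**
- SAP Section 2, Secondary objectives, asks whether the app is comparable "when stratifying by diagnosis (RA, PsA or axSpA"). Protocol 6.7.2 says the same.
- Protocol 6.8 justifies 60 patients by the wish to explore "equivalence margins, within each disease group (i.e. RA, PsA and SpA) separately, a sample size of" 20 pairs each. The SAP's sample-size text repeats this.
- SAP Section 3, Framework, names the comparison stratified by the three diagnoses and then commits to equivalence testing for the outcomes it has listed.
- Randomisation uses three independent schedules, one per diagnosis (protocol 6.9.1; SAP Section 3).

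**What is specified**
- SAP Section 6, Analysis methods: for a continuous "dependent variable (e.g. HAQ-DI), our modelling component of SAS PROC MIXED will include" fixed effects for period, device and diagnosis, with a random participant effect. The model under Outline Table 2 adds a period-by-device term and a baseline term. Neither version has a device-by-diagnosis term.
- SAP Section 6, Additional analyses: the diagnosis subgroup for HAQ-DI is "RA versus other (i.e. PsA or axSpA"), with p < 0.10 as the signal.
- Outline Table 2: HAQ-DI stands only among the general outcomes. The disease-specific rows are DAS28crp (RA and PsA) and BASDAI, BASFI and ASDAS (axSpA).

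**The concern.** With diagnosis as a main effect only, the model lets the HAQ-DI level differ between diagnoses but forces one common device difference on all three. The subgroup contrast then merges two of the three randomisation strata. A test of whether RA differs from the rest is also not an assessment of equivalence within any diagnosis. An analyst who follows the specified models and the legible table shells therefore produces no HAQ-DI device difference for PsA alone or axSpA alone.

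Two things are at stake. A device effect present in only one of these two diagnoses is diluted by the other. And the question that justified 24 of the 60 patients (60 − 36) has no prespecified HAQ-DI analysis in two of three diagnoses, so whether and how to report it would be decided after the data are seen.

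**Working it through.** **Inputs** (protocol 6.8; SAP Sections 3 and 6)
- Sample size: "two one-sided tests analysis for additive equivalence of paired means with bounds -0.11 and 0.11", with "a significance level of 0.05, assuming a mean difference of 0 HAQ-DI points", common SD 0.62, correlation 0.95.
- Decision rule: "equivalence is declared if the entire 2-sided 95%CI is included within the equivalence margin". This corresponds to one-sided tests at 0.025, whereas the sample size uses 0.05 per side.
- 20 pairs per diagnosis, 60 in total.

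**SD of the paired difference:** 0.62 × √(2 × (1 − 0.95)) = 0.196.

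**The plan's own figures.** Exact paired TOST power is the probability that |mean difference| + t × s/√n stays below 0.11, integrated over the distribution of s. With a true difference of 0 and 0.05 per side:

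| Pairs | Stated | Recomputed |
|---|---|---|
| 29 | 80.7% | 80.7% |
| 36 | 90.2% | 90.2% |
| 60 | 99.2% | 99.2% |

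All three reproduce. They apply to the pooled sample; no power is stated for a single diagnosis.

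**One diagnosis, 20 pairs**
- SE = 0.196/√20 = 0.0438.
- 95% half-width: 2.093 × 0.0438 = 0.092 with the stratum's own variance (19 df), or 2.002 × 0.0438 = 0.088 with a variance pooled over the three strata (57 df).
- Power under the 95% CI rule: 33.9% (19 df) to 38.8% (57 df). At the planning level of 0.05 per side it is 56.1% (19 df).
- If the correlation is varied, as an assumption, from 0.90 to 0.97, power under the 95% CI rule (19 df) runs from 2.7% to 73.4%.

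**Illustration: a true difference of 0.15 in axSpA, none in RA or PsA.** The 0.15 is an assumption, chosen because it lies outside ±0.11. The intervals below are at the expected estimates and use SD 0.196.
- Overall: 0.15/3 = 0.05. Half-width 2.001 × 0.196/√60 = 0.051. CI about −0.001 to 0.101, inside ±0.11.
- PsA and axSpA combined: 0.15/2 = 0.075. Half-width 2.023 × 0.196/√40 = 0.063. CI about 0.012 to 0.138.
- RA against the rest: difference 0.075, SE = 0.196 × √(1/20 + 1/40) = 0.0537, ratio 1.40. This is below the 1.645 that roughly corresponds to p < 0.10, so the contrast would not be expected to flag it.
- axSpA alone: 0.15 ± 0.092, CI about 0.058 to 0.242. It excludes zero and extends well beyond 0.11.

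**How often the pooled analysis still declares equivalence in this case:** about 64% if the SD of the difference stays at 0.196, and about 60% if the unmodelled heterogeneity is allowed to enlarge it. The enlarged SD is √(0.196² + 0.15² × (1/3) × (2/3)) = 0.208.

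**The case against.** The strongest reply is that the stratified analysis has not been dropped. The secondary objective and the Framework section both commit to it, and the Framework says equivalence will be tested. The RA-against-the-rest contrast belongs to an exploratory search for contextual factors, is acknowledged to be underpowered, and does not claim to implement the stratified objective. Its RA arm would give an RA estimate. Outline Table 2 also has device comparisons within each diagnosis. Since CRP and joint counts are fixed, DAS28crp varies only with VAS global, so RA and PsA each have a patient-reported comparison of a kind. All of this stands. A reader might infer that the per-diagnosis objective is abandoned or can never be answered; the documents do not support that. They leave a gap between the stated aim and the specified analysis, for HAQ-DI in PsA and in axSpA.

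A reader might also cite Outline Table 3 as proof that diagnosis has only two levels. That table is damaged in the available text and the footnote to its diagnosis row is missing, so nothing here rests on it.

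Nor is every diluted effect a missed one. A difference of 0.10 in one diagnosis lies inside the plan's own margin. A difference of a full MID (0.22) in axSpA alone gives 0.073 ± 0.051 overall, with an upper limit of 0.124, so at the expected estimate overall equivalence would fail. On the same reckoning the range that can hide runs from 0.11 to about 3 × (0.11 − 0.051) = 0.18.

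Finally, the sample-size text promises only an attempt to explore. That limits the weight of the point, but an exploratory aim still needs a defined estimate.

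**Conclusion.** The point holds as an inconsistency. The objectives, Framework and sample-size rationale call for three diagnosis-specific comparisons, while the model, the subgroup list and Outline Table 2 specify no HAQ-DI difference for PsA alone or axSpA alone. The pooled primary analysis remains valid for the question it asks.

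The practical size is moderate: a 0.15 difference confined to axSpA would pass the pooled equivalence rule about 60 to 64% of the time. This depends on SD 0.62, correlation 0.95, 20 complete pairs per diagnosis and an effect in one diagnosis only. Separate rows would not support firm equivalence claims either, with 34 to 39% power each when the true difference is zero. Their value is in showing where a difference lies and how precisely it is known.

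**What to change.** Keep the RA-against-the-rest contrast and add to SAP Section 6:
- a device-by-diagnosis term on the three randomisation strata, or three stratum models;
- the HAQ-DI app-minus-touchscreen difference with its 95% CI, shown against ±0.11, for RA, PsA and axSpA, with the interaction test;
- three matching rows in Outline Table 2 or 3;
- a statement that these are exploratory estimates, giving the expected half-width of about 0.09 and power of about 34 to 39% under the 95% CI rule, so that a CI crossing the margin in one diagnosis is not read as evidence of disagreement.

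The cost is one model term (or three short models) and three table rows. It needs no new data and leaves the primary analysis as it is.

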A: Patient do not complete first device registration, incomplete first data registration, withdrawal/lost to follow-up.

B: Patient do not complete second device registration, incomplete second data registration, withdrawal/lost to follow-up. > 20 $N_0 >> 20$ N = 20 $N_2 > 20$ A PsA æ ź A В Completet n < 10 AD n ≤ 10 $n \le 10$ TS Interested but informed Disease duration < 12 months Technical smartphone Unable to visit clinic in maj-september 2019 Not answering phone Not answering phone consent not obtained < 3 registrations in DANBIO Smartphone cannot Not interested download apps Completet n < 10 TS n ≤ 10 $n \le 10$ AD $N_0 >> 20$ $N_1 > 20$ $N_2 > 20$ = 20Þ В RA ٨ 8 Z Completet $n \le 10$ $n \le 10$ Randomised n < 10AD Screening TS Telephone Telephone Contact 1 Contact 2

Draft Outline Figure 1: Simulated Data

[figure not shown]
Statistical Analysis Plan for the DANBIO app versus touchscreen agreement trial, version 1.0, November 7th 2019. Page: 19

Outline Table 1: Patient demographics and clinical characteristics

Variable 1: Patient demograph	$AD \rightarrow TS$	$TS \rightarrow AD$	All
General characteristics		15 / AD	All
Male, n (%)			
Age (years)			
Disease duration (years)			
Current csDMARD, n (%)			
One csDMARD, n (%)			
Two csDMARDs, n (%)			
Three csDMARDs, n (%)			
MTX, n (%)			
MTX dose (mg/week)			
Oral steroids, n (%)			
Current bDMARDs or tsDMARDs, n (%)			
Last VAS physician			
Last CRP (mg/L)			
PROM			
HAQ-DI			
VAS pain			
VAS fatigue			
VAS global			
PASS "Yes", n (%)			
Anchoring question			
Disease specifics			
Diagnosed with RA, n (%)			
IgM-RF positive, n (%)			
ACPA positive, n (%)			
Erosive, n (%)			
Last tender joint count			
Last swollen joint count			
Last Das28crp			
Diagnosed with PsA, n (%)			
Erosive, n (%)			
Last tender joint count			
Last swollen joint count			
Last Das28crp			
riagnosed with axSpA, n (%)			
Ankylosing spondylitis, n (%)			
BASDAI			
BASFI			
HLA-B27 positive, n (%)			
Sacroiliitis on x-ray, n (%)			
Last tender joint count			
Last swollen joint count			
Last BASMI			
Last ASDAScrp			-

AD: app device, TS: touchscreen solution. For continuous outcomes values will be reported as means and SDs, unless otherwise stated.

Draft Outline Figure 2: Simulated Data for Bland-Altman Plot

Statistical Analysis Plan for the DANBIO app versus touchscreen agreement trial, version 1.0, November 7th 2019. Page: 21

Outline Table 2: Comparison between groups for all PROM and clinical outcomes.

^d: Analysed as: 1) DAS28crp for RA and PsA and 2) ASDAS for axSpA.
